Approximate Duration of Study	5years
Dosage and Administration	PIO 30mg/d, 45mg/d, oral tablets
Concomitant Medications/treatment	TKI
Safety Evaluations	Monthly assessments as needed with CTCAE v. 4.0
Statistical Analysis	
Under Simon's optimal two stage design with a 5% significance level, 80% power, and 8% drop out rate assuming a lower boundary of interest in the response rate of 20% and an upper boundary of interest in the response rate of 50%, a total of 26 evaluable subjects are required for the evaluation of the primary endpoint; 9 in Stage 1, additional 15 in Stage 2 and 2 for drop out.
 
If less than 2 of 9 evaluable subjects in Stage 1 maintain MMR after second-TKI discontinuation or > 2 subject develop > grade 3 cardiac toxicity then the study will terminate, otherwise the study shall continue as planned and enrollment of an additional 15 subjects shall continue into Stage 2. If, at the final analysis, less than 9 of 24 evaluable subjects in both Stage 1 and 2 maintain MMR then it will be concluded that PIO and TKI does not deserve further investigation.
 
Fisher exact test and the χ^2 test were used to compare categorical variables, and the Mann-Whitney U test was used for continuous variables. The probability of molecular relapse free survival will be estimated using the Kaplan-Meier method, and be calculated as the time from the first day of TKIs discontinuation to the date of the first documentation of molecular relapse or the last follow up day for patients who did not relapse. $P < 0.05$ will be considered statistically significant.

ABBREVIATIONS

2G	Second-Generation
AE	Adverse Event
AP	Accelerated Phase
AUC	area under the curve
BC	Blast crisis
BM	Bone Marrow
BOS	Bosutinib
BP	Blood Pressure
CBC	Complete Blood Count
CCyR	Complete Cytogenetic Response
CHR	Complete Hematologic Response
CLcr	Creatinine Clearance
Cmax	Peak Serum Concentration
Cmin	Trough Serum Concentrations
CML	Chronic Myeloid Leukemia
CMR	Complete molecular remission
CP	Chronic Phase
CRF	Case Report Form
CTCAE	Common Terminology Criteria for Adverse Events
DAS	Dasatinib
DSMC	the Data and Safety Monitoring Committee
ELN	European Leukemia Net
FDA	Food and Drug Administration
GCP	Good Clinical Practice
HCG	Human Chorionic Gonadotropin
ICH	International Conference on Harmonization
IRB	Institutional Review Board
IS	International Scale
IM	Imatinib Mesylate
IND	Investigational New Drug
LSC	Leukemia Stem Cell
mCyR	minor Cytogenetic Response

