1.6 Rationale for the Study

New approaches are needed for the management of the 50% of CML patients who experience a molecular relapse following a first trial of TKI discontinuation. Given the potential risks of long-term TKI exposure, the contra-indication for pregnancies/child conception while on TKI, and the expenses associated with the use of these agents (92,000 USD/year for IM, > 120,000 USD/year for DAS or NIL), many patients express interests in TKI discontinuation trials. However, with the low success rate of a second discontinuation trial (20%), patients who fail their first TKI discontinuation have currently no other option but to continue TKI therapy.

Given the interactions between PPAR γ and STAT5 in CML LSCs, the synergy between PIO and IM [41], and the safety profile of PIO, a trial testing the combination of PIO and TKIs is a reasonable novel approach to eradicate minimal residual disease in CML .

2. Study Objectives and Hypothesis

2.1 *Objectives*

- To assess safety of the combination of PIO and TKI in CML subjects who experience a loss of MMR following a first TKI discontinuation
- To assess survival without loss of MMR following a second TKI discontinuation in subjects who achieve or maintain \leq MR^{4,5} with the combination PIO and TKI administered for at least 6 months

2.2 *Hypothesis*

Subjects who lose MMR after a first TKI discontinuation trial, but are still in CCyR and CHR regardless of their molecular status, will be offered enrollment on this trial. We hypothesize that PIO in combination with TKI will be well tolerated and that subjects will achieve or maintain \leq MR^{4,5} with the combination of TKI and PIO. Subjects who achieve \leq MR^{4,5} will be offered a second TKI discontinuation trial. We also hypothesize that MMR will be sustained following a second TKI discontinuation in at least 50% of subjects.

3. Investigational Plan

3.1 *Overall Study Design and Plan*

This is an open-label phase 2 study in which eligible subjects will receive PIO in combination with TKI. Safety of PIO in combination with TKI will be assessed continuously. Subjects who lose MMR while on the combination will be taken off study and managed at the discretion of the treating physician. Loss of MMR is defined by a detectable *BCR-ABL1* level $>0.1\%$ and confirmed within 4 weeks. For the purposes of this protocol and all analyses, a cycle of treatment is defined as 28 days. Study schema is depicted in Figure 7.

[figure not shown]

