Figure 7. Study schema

Subjects may enter the study before or after restarting the TKI that was previously discontinued. Disease status can therefore be $>$ MMR but still in CCyR and CHR or \leq MMR. Subject will start PIO in addition to TKI, at 30mg/d for 2 cycles (56 days) and, in the absence of grade 2 or higher toxicities, PIO doses will be increased to 45mg/d. If grade 2 or higher toxicities occur on PIO 45 mg/d, PIO dose will be held until toxicities are \leq grade 1, and PIO doses will be decreased to 30 mg/d (**Dose modification was described section 7.1**). Subjects will receive PIO in addition to TKI for 6 months from the first documented \leq MR^{4,5}. During the combination of PIO and TKI, subjects will be monitored by blood qRT-PCR for *BCR-ABL1* obtained monthly.

Subjects entering the study in $>$ MMR but still in CCyR and CHR who do not achieve MMR within 4 months of the combination of PIO and TKI will be taken off study. Subjects entering the study in \leq MMR or who achieve MMR within 4 months of combination of PIO and TKI, will receive PIO for 6 months from the first documented \leq MR^{4,5}. Subjects who lose MMR at any time on the combination of PIO and TKI will be taken off treatment. Subjects who fail to achieve \leq MR^{4,5} after 6 months of the combination will also be taken off treatment. Fluctuations of PCR from MR^{4,5} at \leq MMR levels are expected and are acceptable during the combination of PIO and TKI.

Subjects who maintain \leq MR^{4,5} for 6 months with less or equal than 2 *BCR/ABL1* transcript fluctuation $<$ MMR will be eligible for a second TKI discontinuation trial. Subjects who discontinue TKI will be monitored by blood qRT-PCR for *BCR-ABL1* obtained monthly for the first 3 months, quarterly for 1 year, and then bi-annually for 1 year. After 2 years of follow-up off TKI, or if MMR is lost off TKI, subjects will have completed their participation on the trial and will enter the Long-Term Follow-up which includes once a year update on disease status (qRT-PCRs) for 5 years.

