- Review and document all inclusion and exclusion criteria to ensure that subjects meet all inclusion criteria and none of the exclusion criteria.
- Record AEs as part of standard of care.
- Dispense PIO at 30 mg/d and instruct subjects how to take study drug, daily every 24 hours and how to fill the diary card.

5.2.3 **Visits 3 (Days 14 \pm 2): Early Follow-up**

- Measure and record height in cm and weight in kg. Record vital signs. Measure body temperature, systolic/diastolic BP and pulse rate. Perform and record physical examination.

- Record medications including start/stop dates, indication, dose and frequency for any changes since previous visit.
- Collect blood samples for CBC with differential count and serum chemistries.
- Assess study drug compliance by pill count, review of the diary card and MMAS-8.
- Assess and record AEs and SAEs

5.2.4 Visits 4+ (Day 28 ±2, then q28+/-2 days during combination of PIO and TKI)

- On day 28, measure and record height in cm and weight in kg. Record vital signs. Measure body temperature, systolic / diastolic BP and pulse rate. Perform and record physical examination. Unless new symptoms occur, these will be performed every other month as part of standard of care.
- On day 28, record medications including start/stop dates, indication, dose and frequency for any changes since previous visit. Unless new symptoms occur, these will be performed every other month as part of standard of care.
- On day 28, collect blood samples for CBC with differential count and serum chemistries. Unless new symptoms occur, these will be performed every other month as part of standard of care.
- On day 56, in the absence of grade 2 or higher toxicities, PIO doses will be increased to 45 mg/d
- Dispense drug supply for self-dosing, remind subjects of dosing instructions, and obtain all unused study drug
- Assess study drug compliance by pill count, review of the diary card and MMAS-8.
- Collect blood samples for qRT-PCR of *BCR/ABL1* every month.
- Assess and record AEs and SAEs continuously

5.2.5 Post-discontinuation of PIO and TKI Visits (Monthly for 3 months ± 2 days and quarterly ±7 days for 1 year and biannually thereafter)

- Collect blood samples for qRT-PCR of *BCR/ABL1* as part of standard of care
- Assess and record AEs and SAEs continuously

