5.2.6 Unscheduled Visits

Unscheduled visits may occur at any time at the investigator's discretion, and appropriate clinical and laboratory measurements performed based on AEs or other findings.

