5.2.7 End of Treatment Visit (±14 days)

At the time of last study monitoring, loss of MMR, failure to achieve <MMR after 4 months or < MR^{4,5} after 6 months of combination treatment of PIO and TKI, the End of Treatment Visit should be completed for all subjects as soon as possible, and every effort should be made to perform the procedures required. Subjects will also return to the clinic or will be contacted for a safety follow-up assessment 30 days ± 3 days after the last dose of study drug was taken. Only information about AEs and SAEs will be collected at this visit.

The following procedures will be performed at End of Treatment Visit:

- Measure and record height in cm and weight in kg. Record vital signs. Measure body temperature, systolic / diastolic BP and pulse rate. Perform and record physical examination which is part of standard of care
- Record medications including start/stop dates, indication, dose and frequency for any changes since previous visit.
- Collect blood samples for CBC with differential count, blood chemistries, and qRT-PCR of *BCR/ABL1* as part of standard of care
- Collect blood samples for ABL1 domain mutation analysis as part of standard of care in case of loss of MMR
- Obtain all unused study drug if subjects drop out before discontinuation of PIO and TKI.
- Assess study drug compliance by pill count and review of the diary card
- Assess and record AEs and SAEs

5.3 *Subject Registration and Identification*

Demographic information on all subjects who sign the Informed Consent Form will be recorded on the master subject log. Those subjects who complete screening procedures and meet all eligibility criteria may be enrolled. At the time of registration, the subject will be assigned a unique identification code (number), consisting of a study site number and a unique consecutive number.

5.3.1 *Screen Failure*

Subjects who have signed informed consent and subsequently fail to meet the inclusion and/or exclusion criteria are defined as screen failures. For all screen failures, the Investigator is to maintain a screening log that documents the subject initials and reason(s) for screen failure. A copy of the log will be retained in the Investigator's study files. Any subject who is rescreened after screen failure must, in addition to the failed procedure, repeat only those screening procedures outlined in the Schedule of Events that have fallen outside the specified screening period.

5.3.2 *Early Discontinuation*

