9.4 Determination of Sample Size

Previous reports suggest that PIO is well tolerated at the doses of 30 and 45 mg [47]. Under Simon's optimal two stage design with a 5% significance level and 80% power, assuming a lower boundary of interest in the response rate of 20% and an upper boundary of interest in the response rate of 50%, a total of 24 evaluable subjects are required for the evaluation of the primary endpoint; 9 in Stage 1 and an additional 15 in Stage 2. If $\leq 2/9$ evaluable subjects in Stage 1 maintain MMR after second-TKI discontinuation or ≥ 2 subject develop \geq grade 3 cardiac toxicity then the study will terminate, otherwise the study shall continue as planned and enrollment of an additional 15 subjects shall continue into Stage 2. If, at the final analysis, less than 9 of 24 evaluable subjects in both Stage 1 and 2 maintain MMR then it will be concluded that the combination of PIO and TKI does not deserve further investigation. After adjusting for 8% drop out rate, the actual required sample size will be 26 subjects. Therefore, the total sample size of the study will be 26 subjects.

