9.5 Safety and Efficacy Analysis

All subjects receiving at least 1 dose of study drug will be considered evaluable for safety. Listings of laboratory test results will also be generated, and descriptive statistics summarizing the changes in laboratory tests over time will be presented. Exposure to study drug over time will also be summarized. The AE incidence rates, as well as the frequency of occurrence of overall toxicity, categorized by toxicity grades (severity) will be described. The number of subjects that has reappearance of *BCR-ABL1* will be described. Descriptive statistics that will summarize the changes in *BCR-ABL1* testing over time will be presented. Loss of MMR is defined as a *BCR-ABL1* $>0.1\%$ by qRT-PCR confirmed within a week and associated with a rise in the titer on a confirmatory test obtained 4 weeks later (ELN definition). For the primary and secondary efficacy endpoints, subgroup analyses will be performed by baseline potential prognostic factors. Subgroups will include: age, gender, race, underlying diagnosis, and other disease-related prognostic factors (disease status).

9.6 *Interim Analysis*

An interim analysis is planned after 9 subjects have been enrolled and their results have been obtained. This interim analysis will focus on efficacy as discussed in section 9.4 and safety. If grade 3-4 toxicity is observed at any moment in 2 subjects, the trial will be put on hold and no further subjects will be enrolled until analyses of these cases is complete and reviewed by the data safety monitoring board (**DSMB**).

9.7 *Protocol Deviations and Violations*

To be protocol-compliant, a subject must not have any major protocol deviations during the study period. Protocol deviations will be identified prior to final analysis and will be listed by treatment group in the clinical study report.

10. Quality Control and Quality Assurance and Study Monitoring

The investigator is responsible for performing quality control and assurance checks. Before enrolling any subjects into this study, the investigator will review the protocol, the CRFs and instructions for their completion, the procedure for obtaining informed consent, and the procedure for reporting AEs with all personnel listed on the delegation of authority and FDA1572. The investigator will evaluate the conduct of the trial at least once monthly and perform the following:

- Review information recorded in the CRFs and verify against source documents

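### Loss of MMR has two differing definitions (3.1 and a stricter 9.5); the 9.4 decision counts and the Kaplan-Meier analysis cite neither, and the visit schedule does not supply the tests that 9.5 needs

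*Combined protocol and SAP*

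**What the plan says.** Section 3.1 (Overall Study Design and Plan) defines loss of MMR as a level above 0.1% "and confirmed within 4 weeks". No rise is needed.

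Section 9.5 (Safety and Efficacy Analysis) uses the same threshold but wants it "confirmed within a week and associated with a rise in the titer on a confirmatory test obtained 4 weeks later (ELN definition").

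Section 9.4 concludes that the combination does not merit further study if "less than 9 of 24 evaluable subjects in both Stage 1 and 2 maintain MMR", and it stops at Stage 1 if 2 or fewer of 9 do so. The synopsis runs the Kaplan-Meier time to "the date of the first documentation of molecular relapse". None of these passages points to 3.1 or 9.5.

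Off-TKI qRT-PCR is scheduled in 5.2.5 as "Monthly for 3 months ± 2 days and quarterly ±7 days for 1 year and biannually thereafter". Section 5.2.6 adds that "Unscheduled visits may occur at any time", at the investigator's discretion. The End of Treatment visit (5.2.7), which includes a qRT-PCR, falls "At the time of last study monitoring, loss of MMR", among other triggers. Section 3.1 adds that after 2 years off TKI "or if MMR is lost off TKI, subjects will have completed their participation on the trial"; the subject then moves to yearly updates.

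**The concern.** The stop/go counts and the relapse-free survival curve both rest on one event, and that event has two definitions. The choice stays open until someone makes it, possibly with results in view. With cut-offs at 3/9 and 9/24, a single subject classified differently can change a decision.

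The stricter definition also depends on tests that the calendar does not supply. No rule says how to classify a subject with a value above 0.1% whose confirmatory tests were not done. On a literal reading of 9.5 such a subject has not lost MMR, so a gap in testing would count in favour of the treatment.

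**Working it through.** **1. How the definitions relate.** Confirmation within one week is also confirmation within four weeks, and 9.5 adds a further condition. So every 9.5 loss is a 3.1 loss, but not the reverse, and on the same results the number maintaining MMR under 9.5 is equal or higher. Example: 0.15%, then 0.14% within a week, then 0.12% four weeks later. This is a loss under 3.1. It is not a loss under 9.5 if the rise is measured from the first value above 0.1%. It is a loss if the rise is measured from the level before MMR was lost. Section 9.5 does not say which.

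**2. Which tests are scheduled off TKI.**

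| First value >0.1% at | Repeat within 1 week | Test about 4 weeks later |
|---|---|---|
| Month 1 or 2 | not scheduled | next monthly sample |
| Month 3 or later | not scheduled | not scheduled |

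The 3.1 confirmation is likewise unscheduled from the month 3 sample on. The End of Treatment qRT-PCR is triggered by loss of MMR itself and is timed to neither 9.5 test, so it does not fill the gap.

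**3. The plan's rule.** Inputs from 9.4: n1 = 9, n = 24, continue if at least 3/9, success if at least 9/24, rates 20% and 50%, planned 5% significance and 80% power. With X1 ~ Bin(9, p) and X2 ~ Bin(15, p):

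P(success) = Σ over x = 3 to 9 of P(X1 = x) · P(X2 ≥ 9 − x)

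This gives 2.9% at p = 0.20 and 86.6% at p = 0.50, so the rule as written meets both planned limits. (The sample size of 24 is not what Simon's optimal search returns for 20% versus 50%; that is a separate matter and nothing below depends on it.)

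**4. Chance of ending one subject short of a cut-off.**

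| Outcome | p = 0.20 | p = 0.50 |
|---|---|---|
| Exactly 2/9 at Stage 1 | 36 × 0.2² × 0.8⁷ = 30.2% | 36 × 0.5⁹ = 7.0% |
| Pass Stage 1, then exactly 8/24 | 3.5% | 2.9% |

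These are chances of being at the boundary. A changed decision also needs a discordant subject. One subject is 1/24 = 4.2 points of the final proportion.

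**5. Illustration with an assumed share f** of 3.1 losses that never meet 9.5. The documents give no f.

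- Planning rates assume 3.1, and 9.5 is applied: the apparent null rate is 0.20 + 0.80f. At f = 0.05 it is 0.24 and type I error is 8.1%. The planned 5% is passed at f of about 2.4%.
- Planning rates assume 9.5, and 3.1 is applied: the rate at the alternative is (0.50 − f)/(1 − f). At f = 0.05 it is 0.45/0.95 = 0.474 and power falls from 86.6% to 81.3%.

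The synopsis and 12.4 word the Stage 1 rule differently (stop if fewer than 2 of 9). On that wording the type I figures are 3.5% and 9.5%. The two Stage 1 wordings must be reconciled in any case.

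**The case against.** The strongest reply is that location settles the matter. The 3.1 definition directly follows a sentence about loss during combination treatment, and its four-week confirmation suits the monthly on-treatment sampling. The 9.5 definition stands in the analysis section, just before the efficacy endpoints are mentioned. On that reading one is an on-treatment rule, the other is the analysis rule, and only a cross-reference is missing. This has force, and 9.5 is the likelier intention. But 3.1 does not limit its definition to the combination phase, and the same section uses loss of MMR off TKI to end participation. Even if 9.5 governs, the reference for the rise and the handling of missing tests remain open.

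A reader might infer that the 9.5 tests are optional. The documents do not support that: the definition itself presupposes them, and tests triggered by a result need not appear in a calendar table. Nor does the end of participation at loss block them, since under 9.5 loss exists only once confirmed. What stands is narrower: no schedule provides the tests, and no rule covers their absence.

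A reader might also take the 30.2% as the chance of a wrong decision, or the 8.1% as the trial's actual type I error. Neither follows. The first is only a boundary probability. The second rests on an assumed share and on permanent reclassification, whereas a subject who does not yet meet 9.5 stays in follow-up and may meet it later.

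**Conclusion.** The point holds. There are two definitions of the decision-relevant event, neither is cited where the event is counted, the stricter one lacks a reference value for the rise, and the schedule does not secure the data it needs. The certain size is one subject: enough to turn 2/9 into 3/9 or 8/24 into 9/24.

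The error-rate figures are illustrations. They assume a 5% share, independent and permanent reclassification, and all 24 evaluable subjects reaching discontinuation; later conversion would shrink them. It would go too far to say that the plan inflates type I error. The direction depends on which definition the 20% and 50% rates assume, and the historical second-discontinuation rates (25% in 1.3, 20% in 1.6) come with no relapse definition.

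A separate minor note, which does not affect the counting of loss of MMR: Table 1 gives MR4.5 as below 0.032%, looser than its own MR4.0 (below 0.01%), while the text beneath gives 0.0032%. A PDF reading error is possible, so the entry should be checked against the source.

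**What to change.** Reconcile 3.1 and 9.5. Before data are reviewed:

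- Name one analysis definition of loss of MMR, including the reference value if a rise is kept, and cite it in 9.4 and in the Kaplan-Meier text.
- For the analysis, count as not having maintained MMR any subject with a value above 0.1% whose confirmatory test is missing, and any subject who restarts TKI for molecular relapse.
- Report the other definition as a sensitivity analysis where the tests exist.

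This concerns the analysis event only. The withdrawal and treatment-stopping rules that use loss of MMR are for the sponsor to reconcile.

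The cost is wording, with no added subjects or scheduled visits. The downside is that the success proportion, and possibly power, may be slightly lower than under a literal reading of 9.5. The missing-confirmation rule is also stricter than either existing definition, since both require confirmation.
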